1.1.3.3. Exploratory Objectives

The exploratory objectives include the following:

- To describe the efficacy of VGX-3100, administered alone or in combination with imiquimod, at Week 74 and/or Week 96 as measured by reduction in the surface area of the qualifying vulvar lesion(s), in subjects without a complete lesion resolution at Week 48
- To describe the long term efficacy of VGX-3100, alone or in combination with prior imiquimod, as measured by histologic regression of vulvar HSIL
- To describe the long term efficacy of VGX-3100, alone or in combination with prior imiquimod, as measured by virologic clearance of HPV-16/18
- To evaluate tissue immune responses to VGX-3100, and VGX-3100 with imiquimod, as measured in vulvar tissue samples
- To describe virologic clearance of HPV-16/18 from non-vulvar anatomic locations
- To describe association of microRNA (miRNA) profile, previous vulvoscopy, and HPV testing results with Week 48 histologic regression
- To describe patient reported outcomes (PRO) for subjects treated with VGX-3100 and VGX-3100 with imiquimod
- To describe the humoral and cellular immune response of VGX-3100 administered alone or in combination with imiquimod, post dose 3, post dose 4, and after additional dosing
- To determine the long term efficacy of VGX-3100 alone or in combination with imiquimod with respect to histopathologic regression of vulvar HSIL or virologic clearance of HPV-16/18 in vulvar tissue

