- Percent reduction in the cumulative surface area of the acetowhite vulvar lesion(s) as determined by the quantitative analysis of standardized pre-biopsy photographic imaging of qualifying lesion(s) at Week 74 and/or Week 96 compared to baseline. Results will be classified as: no clinically significant lesion resolution (reduction in lesion area of 0-25%), partial lesion area resolution (>25% and <100% reduction) and complete lesion resolution (no visible lesion).
- Proportion of subjects with no evidence of vulvar HSIL on histology (i.e. biopsies or excisional treatment) at Week 74 for subjects who receive 5 doses of VGX3100 and at Week 96 for subjects who receive 6 doses of VGX-3100.
- Virologic clearance in vulvar tissue samples at Week 74 and/or Week 96 compared to baseline.
- Virologic clearance from non-vulvar anatomic locations without surgical intervention at Week 48 compared to baseline.

- The relationship of microRNA (miRNA) profile (Day 0, Week 15, and Week 48), previous vulvoscopy, and HPV testing results (vulvar swab and vulvar tissue) with Week 48 histologic regression of vulvar HSIL.
- Proportion of subjects at Week 74 and 96 with no histologic evidence of vulvar HSIL or no evidence of HPV-16/18 in vulvar tissue samples (i.e. collected via biopsy or excisional treatment).

To assess quality of life and related impacts on subjects, patient-reported outcome (PRO) instruments will be provided and will include the Short Form Health Survey version 2 (SF-36v2TM) (Optum), the EQ-5D-5L (EuroQol Research Foundation), WOMAN-PRO (WOMen with vulvAr Neoplasia) Clinical Trial Version 2.0, and 2 additional PRO questions assessing quality of life after surgery or biopsy. The PRO instruments are described below.

- WOMAN-PRO is a 31 item self-completed patient reported outcome measure designed to assess both physical and psychosocial impacts of VIN.
- SF-36v2 generically measures functional health and well-being, for physical and mental health. The questionnaire consists of 36 items covering 8 domains (Physical functioning, Role limitations due to physical problems, Bodily pain, General health, Vitality, Social functioning, Role limitations due to emotional problems, and Mental health).
- EQ-5D-5L generically measures activities and general health status and consists of 6 items covering 6 domains (Mobility, Self-care, Usual activity, Pain/discomfort, Anxiety/depression, and Global health status).

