2. SUBJECT POPULATION

2.1. **Population Definitions**

The following subject populations will be evaluated and used for presentation and analysis of the data:

- Modified Intention-to-Treat (mITT) Population: All subjects who receive at least 1 dose of VGX-3100 + EP and who have the analysis endpoint of interest. Subjects in this sample will be grouped to treatment arms as randomized.
- Per-protocol (PP) Population: All subjects who receive at least 4 doses of VGX-3100 + EP, have no protocol violations, and who have the analysis endpoint of interest. Subjects in this sample will be grouped to treatment arms as randomized. Subjects excluded from the PP population will be identified and documented prior to locking of the study database.
- Safety Population: All subjects who receive at least 1 dose of VGX-3100 (with or without EP). Subjects will be analyzed as to the treatment they received.

The mITT population is the primary population for the analysis of efficacy parameters. The PP population will be considered supportive of the corresponding mITT population for the analysis of efficacy. The Safety population is the primary population for the analysis of safety endpoints.

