4.3. Efficacy Evaluation

Efficacy analyses will be conducted using the mITT population. Supportive analyses of efficacy will be based on the PP population.

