Reduction in surface area of qualifying vulvar lesion(s) at Weeks 48, 74, and 96 will be assessed by treatment group and determined by quantitative analysis of standardized pre-biopsy photographic imaging. The mean percent change and associated 95% t-distribution based CI will be presented. Also, the percent reduction will be classified as no clinically significant lesion resolution (reduction in lesion area of 0-25%), partial lesion area resolution (>25% and <100% reduction), and complete lesion resolution (no visible lesion). A lesion will be considered qualifying if it is confirmed to be HPV-16 and/or HPV-18 positive and have histologically confirmed vulvar HSIL by the PAC at screening. The percentage of subjects in each lesion category will be summarized by treatment group with point estimates and associated exact Clopper-Pearson 95% CIs.

Regression/clearance endpoints will be summarized with the number and percentage of subjects meeting the endpoint separately by previous vulvoscopy results and by previous HPV test results. The relationship between the regression/clearance endpoints with miRNA profiles will be summarized with the median change from baseline in miRNA profiles by those who achieved versus not achieved the endpoint.

By-subject listings will be provided for all efficacy-related parameters and results.

| Table 14.2.2.1A | Incidence of Histologic Regression at Week 48 (mITT Population) |
|-----------------|--------------------------------------------------------------------------------------------------------|
| Table 14.2.2.1B | Incidence of Histologic Regression at Week 48 (PP Population) |
| Table 14.2.2.2A | Incidence of Vulvar Virologic Clearance at Week 48 (mITT Population) |
| Table 14.2.2.2B | Incidence of Vulvar Virologic Clearance at Week 48 (PP Population) |
| Table 14.2.2.3A | Incidence of Histologic Regression or Virologic Clearance at Week 48 (mITT Population) |
| Table 14.2.2.3B | Incidence of Histologic Regression or Virologic Clearance at Week 48 (PP Population) |
| Table 14.2.2.4A | Incidence of Histologic Regression to Normal at Week 48 (mITT Population) |
| Table 14.2.2.4B | Incidence of Histologic Regression to Normal at Week 48 (PP Population) |
| Table 14.2.2.5A | Incidence of Non-progression to Vulvar Cancer at Week 48 (mITT Population) |
| Table 14.2.2.5B | Incidence of Non-progression to Vulvar Cancer at Week 48 (PP Population) |

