| Table 14.2.2.15B | Incidence of Histologic Regression at Week 48 by Previous HPV Test Results (PP Population) |
| Table 14.2.2.16A | Incidence of Histologic Regression at Week 48 by Previous miRNA Profile (mITT Population) |
| Table 14.2.2.16B | Incidence of Histologic Regression at Week 48 by Previous miRNA Profile (PP Population) |
| Table 14.2.2.17A | Incidence of Virologic Clearance at Week 48 by Previous Vulvoscopy Result (mITT Population) |
| Table 14.2.2.17B | Incidence of Virologic Clearance at Week 48 by Previous Vulvoscopy Result (PP Population) |
| Table 14.2.2.18A | Incidence of Virologic Clearance at Week 48 by Previous HPV Test Results (mITT Population) |
| Table 14.2.2.18B | Incidence of Virologic Clearance at Week 48 by Previous HPV Test Results (PP Population) |

| Incidence of Virologic Clearance at Week 48 by Previous miRNA Profile (mITT Population) |
|-----------------------------------------------------------------------------------------|
| Incidence of Virologic Clearance at Week 48 by Previous miRNA Profile (PP Population) |
| Change in Surface Area of Qualifying Vulvar Lesion(s) (mITT Population) |
| Change in Surface Area of Qualifying Vulvar Lesion(s) (PP Population) |
| HPV Testing Results: FFPE Vulvar Tissue Samples |
| HPV Testing Results: Cervical ThinPrep and Swab Samples |
| Cervical Colposcopy and Biopsy Results |
| Vulvoscopy and Biopsy Results |
| Photographic Lesion Results |
| miRNA Profiles by Visit |
| |

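### The Week 74/96 lesion-area objective is limited to subjects not fully resolved at Week 48, but the endpoint and analysis drop that limit, so no listed summary answers it

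*SAP*

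**What the plan says.** The exploratory objective in SAP 1.1.3.3 concerns "reduction in the surface area of the qualifying vulvar lesion(s), in subjects without a complete lesion resolution at Week 48", at Week 74 and/or Week 96. The secondary lesion-area objective in 1.1.3.2 carries no such limit.

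The exploratory endpoint in 1.2.5.1 rests on "quantitative analysis of standardized pre-biopsy photographic imaging of qualifying lesion(s) at Week 74 and/or Week 96 compared to baseline". It does not mention Week 48 status.

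The analysis in 4.3.2 treats all three visits in one sentence: "Reduction in surface area of qualifying vulvar lesion(s) at Weeks 48, 74, and 96 will be assessed by treatment group". For the statistic, "The mean percent change and associated 95% t-distribution based CI will be presented", together with the percentage of subjects in the none, partial and complete categories and exact intervals.

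On the population, 4.3 says "Efficacy analyses will be conducted using the mITT population", with PP as support. Section 2.1 defines mITT as "All subjects who receive at least 1 dose of VGX-3100 + EP and who have the analysis endpoint of interest". The output list in 4.3.2 has one surface-area table for mITT and one for PP.

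**The concern.** One sentence in 4.3.2 serves two objectives with different populations: the unrestricted secondary objective and the restricted exploratory one. The restriction is lost in the merger. A subject with no visible lesion at Week 48 and a later measurement contributes to the Week 74 and Week 96 means, and to the complete-resolution category if still clear.

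The objective asks what happens later to lesions that had not cleared by Week 48. The planned summary describes a mixture of those subjects and the ones who had already cleared. With planned arms of 24 and 12, a few earlier resolvers can move that figure noticeably. A reader who takes the Week 74/96 table as the answer to the objective would be reading a different quantity.

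**Working it through.** **Does anything else in the SAP restore the restriction?**

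- *Population.* mITT requires a dose and an available endpoint. PP adds four doses and no protocol violations. Neither refers to Week 48 lesion status.
- *Data availability.* The schedule in 1.2.4 places vulvoscopy and lesion photography at Weeks 74 and 96, and its photography footnote requires photographs at all vulvoscopy examinations. Subjects clear at Week 48 can therefore be expected to have later data, although the shortening of the study to 78 weeks (1.2.1) thins Week 96.
- *Subgroups.* Section 3.8 promises separate analysis of certain subgroups at later time points but names no endpoint or table. Its grouping also differs. It pairs Subgroups A and B because both lack HSIL, yet by 1.2.1 A has no visible lesion and B has one. Subjects in B, C, D and E can all be unresolved, so C and D alone are not the objective's population.
- *Dose split.* The binary Week 74/96 regression and clearance endpoints in 4.3.2 are split by number of doses received. Lesion area has no split.
- *Declared changes.* Section 5 reports no changes from the protocol-defined analyses, so the SAP does not present this as a deliberate departure.

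None of these supplies the restricted estimate.

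**How far apart can the two means be?** The SAP states no lesion-area figure, so there is nothing to reproduce, and every input below is an assumption. Let f be the share of measured subjects who were clear at Week 48, R their mean reduction at the later visit, and m the mean reduction in the rest.

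- Unrestricted mean = f x R + (1 - f) x m
- Objective's mean = m
- Difference = f x (R - m)

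If earlier resolvers all stay clear (R = 100%):

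| f | m | Unrestricted mean | Difference (points) |
|---|---|---|---|
| 10% | 20% | 28% | 0.10 x 80 = 8 |
| 10% | 40% | 46% | 0.10 x 60 = 6 |
| 20% | 30% | 44% | 0.20 x 70 = 14 |
| 30% | 20% | 44% | 0.30 x 80 = 24 |
| 30% | 40% | 58% | 0.30 x 60 = 18 |

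Over this grid the gap runs from 6 to 24 points. The pooled mean itself runs from 28% to 58%, which is not the size of the discrepancy.

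The direction depends on R. With f = 20% and m = 30%, R = 50% gives 0.20 x 20 = 4 points upward, and R = 20% gives 0.20 x (-10) = 2 points downward.

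**Categories, with assumed counts.** Take 22 measured subjects, roughly 90% of 24. Section 3.1 assumes 90% evaluable at Week 48 only, so carrying it to Week 74 is a further assumption. Suppose 4 were clear at Week 48 and remain so.

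- If 2 more clear later: 6/22 = 27% unrestricted, against 2/18 = 11% in the objective's population.
- If nobody else clears: 4/22 = 18.2% (exact 95% CI 5.2% to 40.3%), against 0/18 (upper limit 18.5%).

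**The case against.** The strongest reply is that the analysis matches its endpoint. Section 1.2.5.1 defines reduction against baseline, not against Week 48, and 4.3.2 carries that out. An unrestricted Week 74 mean is a valid description of status against baseline, including whether earlier resolution lasts. This stands.

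A reader might infer that the plan double-counts Week 48 responders, or credits their resolution as later benefit and so inflates the long-term result. The documents do not support that. Summaries by visit are not double counting, and the upward direction needs R above m, which the SAP does not establish. Nor would the restriction remove all earlier gain: a subject at 90% reduction at both Week 48 and Week 74 stays in the restricted set with that gain counted.

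It can also be said that 4.3.2 does not state that all subjects are included in the lesion-area analysis, that the table shells are in a separate document not at hand (7.2), and that subgroup status and photographic results will be listed by subject. Inclusion is indeed read from the absence of a restriction, and it reaches only mITT or PP subjects with a later measurement. But the titles listed name only those two populations, and rebuilding the subset from listings would be post hoc.

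Finally, the objective could be reworded to match the analysis. That would remove the inconsistency, but it would also give up the question about unresolved lesions.

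**Conclusion.** The point holds as a mismatch between objective and analysis. As written, the plan lists no summary of later lesion-area reduction in the subjects the objective names. The gap between the two means is f x (R - m), illustratively 6 to 24 points, on assumed f of 10-30%, m of 20-40% and lasting resolution in all earlier resolvers. The SAP supplies none of these values, so the range shows what is possible and does not estimate a bias.

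The importance is minor. The objective is exploratory and descriptive, section 3.2 confines formal testing to the primary endpoint, and the Week 48 conclusions are untouched.

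**What to change.** In 4.3.2, state that the analysis for this objective is the Week 74 and Week 96 mean percent change with its CI, plus the resolution categories, in subjects whose qualifying lesions had not completely resolved at Week 48, by treatment group and with that subset's own denominator. Say how a subject with no Week 48 lesion measurement is classed. Keep the unrestricted Week 74/96 summary, labelled as a description of status against baseline.

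The cost is a sentence or two in the SAP and a subset flag with extra rows in the two tables already listed; no new data are needed. The downside is smaller denominators, hence wider intervals, and possibly a less favourable late figure.

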- ³ Screening 12-lead ECG, complete blood count (CBC), serum electrolytes, blood urea nitrogen (BUN), creatinine (Cr), glucose, ALT, CPK and urinalysis performed within 45 days prior to first dose administration.
- ⁴ Negative spot urine pregnancy test is required at screening and prior to each study treatment, vulvoscopy and biopsy/surgical excision.
- ⁵ At least 34 mL (4 x 8.5 mL yellow (ACD) tubes) whole blood and 4 mL serum per time point. At least 68 mL whole blood and 8 mL serum should be collected prior to first dose. One additional 8.5 mL yellow (ACD) tube to be collected at Day 0, Week 15 and 48 for microRNA analysis.
- ⁶ At least 51 mL [6 x 8.5 mL yellow (ACD) tubes] whole blood and 4 mL serum should be collected at Week 27.
- ⁷ Cervical colposcopy will be performed once at Day 0, and once at Week 96. For subjects completing the study at Week 78, the repeat cervical colposcopy will be performed at Week 74 or the discharge visit.
- ⁸ HPV genotyping and Pap smears are performed on the same ThinPrep® cervical specimen.
- ⁹ An additional visit may be scheduled to perform vulvoscopy if worsening of disease is suspected. Biopsies should not be performed at any visit other than at entry (Screening), Week 48, Week 74 and Week 96 for subjects in Subgroups C and D prior to Amendment 5.0 unless the Investigator suspects invasive cancer. All biopsy samples and/or excision samples obtained prior to or at the subjects final discharge visit (if not a phone visit) must be sent to the PAC for review.
- ¹⁰ Photography of the acetowhite stained qualifying lesion(s) must be performed prior to and after biopsy, and at all vulvoscopy examinations. If a pre-biopsy digital photograph is not available for a historical biopsy sample at screening, a post biopsy photo will be sufficient. Additionally, standardized high resolution digital photographic imaging should be obtained during examinations of the vagina if lesions are identified, for documentation.
- ¹¹ Tissue specimen from all excised tissue obtained prior to or at the subjects in-person discharge visit must be reviewed by the PAC and will be sent to the central laboratory for HPV testing. All lesions will be biopsied at Week 48, 74, and 96 (as applicable), per Amendment 5.0.
- ¹² HPV genotyping is performed on vulvar tissue specimen using a PCR based assay.

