3.4. Baseline Definitions

For all analyses, baseline will be defined as the most recent measurement prior to the first administration of study drug.

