| Table 14.2.2.6A | Incidence of Virologic Clearance Outside of the Vulva at Week 48 (mITT Population) |
| Table 14.2.2.6B | Incidence of Virologic Clearance Outside of the Vulva at Week 48 (PP Population) |
| Table 14.2.2.7A | Incidence of Histologic Regression and Virologic Clearance at Week 74 and Week 96 (mITT Population) |
| Table 14.2.2.7B | Incidence of Histologic Regression and Virologic Clearance at Week 74 and Week 96 (PP Population) |
| Table 14.2.2.8A | Incidence of Histologic Regression at Week 74 and Week 96 (mITT Population) |
| Table 14.2.2.8B | Incidence of Histologic Regression at Week 74 and Week 96 (PP Population) |

| Table 14.2.2.9A | Incidence of Vulvar Virologic Clearance at Week 74 and Week 96 (mITT Population) |
|------------------|--------------------------------------------------------------------------------------------------------------------------|
| Table 14.2.2.9B | Incidence of Vulvar Virologic Clearance at Week 74 and Week 96 (PP Population) |
| Table 14.2.2.10A | Incidence of Histologic Regression or Virologic Clearance at Week 48, Week 74, and Week 96 (mITT Population) |
| Table 14.2.2.10B | Incidence of Histologic Regression or Virologic Clearance at Week 48, Week 74, and Week 96 (PP Population) |
| Table 14.2.2.11A | Incidence of Histologic Regression and Virologic Clearance at Week 48 by Previous Vulvoscopy Result (mITT Population) |
| Table 14.2.2.11B | Incidence of Histologic Regression and Virologic Clearance at Week 48 by Previous Vulvoscopy Result (PP Population) |
| Table 14.2.2.12A | Incidence of Histologic Regression and Virologic Clearance at Week 48 by Previous HPV Test Results (mITT Population) |
| Table 14.2.2.12B | Incidence of Histologic Regression and Virologic Clearance at Week 48 by Previous HPV Test Results (PP Population) |
| Table 14.2.2.13A | Incidence of Histologic Regression and Virologic Clearance at Week 48 by Previous miRNA Profile (mITT Population) |
| Table 14.2.2.13B | Incidence of Histologic Regression and Virologic Clearance at Week 48 by Previous miRNA Profile (PP Population) |
| Table 14.2.2.14A | Incidence of Histologic Regression at Week 48 by Previous Vulvoscopy Result (mITT Population) |
| Table 14.2.2.14B | Incidence of Histologic Regression at Week 48 by Previous Vulvoscopy Result (PP Population) |
| Table 14.2.2.15A | Incidence of Histologic Regression at Week 48 by Previous HPV Test Results (mITT Population) |

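### The stated miRNA summary (change from baseline by response) cannot show whether the Day 0 profile differs by response, and the six listed miRNA tables are titled for a different analysis with undefined groups

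*SAP*

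**What the plan says.** The exploratory objective (SAP section 1.1.3.3) is "To describe association of microRNA (miRNA) profile, previous vulvoscopy, and HPV testing results with Week 48 histologic regression". The matching exploratory endpoint, under Efficacy Parameters (section 1.2.5.1), names three time points: "The relationship of microRNA (miRNA) profile (Day 0, Week 15, and Week 48), previous vulvoscopy, and HPV testing results", each to be related to histologic regression at Week 48.

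Note 5 to the schedule of assessments (Table 1-1) provides blood for exactly those visits: "One additional 8.5 mL yellow (ACD) tube to be collected at Day 0, Week 15 and 48 for microRNA analysis".

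The method is one sentence in section 4.3.2. The relationship between the regression/clearance endpoints and miRNA "will be summarized with the median change from baseline in miRNA profiles by those who achieved versus not achieved the endpoint". Section 3.4 says that "baseline will be defined as the most recent measurement prior to the first administration of study drug".

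The outputs listed in section 4.3.2 include Table 14.2.2.13A, "Incidence of Histologic Regression and Virologic Clearance at Week 48 by Previous miRNA Profile (mITT Population", and Table 14.2.2.16A, "Incidence of Histologic Regression at Week 48 by Previous miRNA Profile (mITT Population". Each has a per-protocol counterpart. A further pair with the same form of title, for virologic clearance, follows Table 14.2.2.18B.

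**The concern.** Two things do not fit together.

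- The endpoint concerns the profile at three visits, one of them before treatment. The method uses only change from that pre-treatment value. Day 0 is the only sample that could describe a characteristic present before dosing, and a change score removes it.
- The text summarises miRNA within response groups. The table titles call for response rates within miRNA groups. To fill the tables as titled, someone must decide which miRNAs count, at which visit and at what cut-off. The SAP fixes none of these, so in an open-label study they could be chosen after response is known.

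At stake is whether a descriptive, hypothesis-generating result can be produced as planned and read without doubt about how its groups were formed.

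**Working it through.** The SAP gives no figure to reproduce here. The check compares the sections and adds one line of algebra.

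**1. What baseline is for miRNA.** Section 3.4 takes the last value before the first dose. Table 1-1 note 5 draws miRNA blood at Day 0, Week 15 and Week 48. Only the Day 0 sample can precede the first dose, so baseline is Day 0.

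**2. What the stated summary can show.** Let X(t) be a subject's level of one miRNA at visit t. The analysed quantity is

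C(t) = X(t) − X(0).

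- At Day 0, C(0) = X(0) − X(0) = 0 for every subject, whatever the response.
- At Weeks 15 and 48, suppose every responder starts at level a, every non-responder starts at level b, and all change by d. The median change is (a + d) − a = d in responders and (b + d) − b = d in non-responders. The summary shows no difference, however far apart a and b are.

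So the stated method carries no information on whether the Day 0 level itself differs by response. Weeks 15 and 48 enter only as differences from Day 0.

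**3. Endpoint against method.**

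| Time point in section 1.2.5.1 | Level by response status | Change by response status |
|---|---|---|
| Day 0 | not stated | zero by construction |
| Week 15 | not stated | possible, but the sentence names no visit |
| Week 48 | not stated | possible, but the sentence names no visit |

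The sentence also does not say how a profile of several miRNAs becomes one median. It applies to all the regression/clearance endpoints, whereas the objective and endpoint name histologic regression only.

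**4. Method against listed tables.**

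| | Grouped by | Quantity summarised |
|---|---|---|
| Text, section 4.3.2 | endpoint achieved or not | median change in miRNA |
| Six table titles | previous miRNA profile | incidence of response |

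Three endpoints in two populations give 3 × 2 = 6 tables. In the text, incidence by group is planned for previous vulvoscopy and previous HPV results, and miRNA gets its own sentence with another method. The miRNA titles nevertheless follow the vulvoscopy and HPV pattern. No listed title names a change in miRNA. The SAP states no miRNA category, cut-off or marker selection, and does not tie the word previous to Day 0 or to Week 15. Neither analysis can be produced from the specification of the other.

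**5. Where Day 0 values do appear.** A listing of miRNA profiles at each visit is planned. Its title does not relate the values to response.

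**The case against.** The strongest reply is that this is an exploratory, descriptive item. Section 3.2 confines formal testing to the primary endpoint, and the Day 0 values will be in a listing from which they can be tabulated later. That stands, and it sets the grade at minor. It does not supply a summary that answers the endpoint.

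A second reply is that the three visits in the endpoint may simply list the sampling times, all of which are used once Day 0 serves as baseline. This is possible, but the objective and the endpoint both speak of the profile, not of change in it.

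A reader might infer four stronger points. The SAP does not support them.

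- *That Day 0 is never related to response.* The incidence titles could cover a Day 0 profile if groups were defined. What can be shown is that the stated method does not do it and that no groups are given.
- *That the table shells contradict the text.* Section 7.2 places the shells in a separate document. Only titles can be compared, and the shells may define groups.
- *That treatment arm is ignored.* Section 3.2 already has summaries presented by treatment group and overall as applicable.
- *That any cut-off chosen afterwards would put all responders on one side.* Using section 3.1, evaluable subjects are 0.9 × 24 = 21.6 and 0.9 × 12 = 10.8, about 22 and 11. Expected responders are 0.20 × 21.6 = 4.3 and 0.28 × 10.8 = 3.0, about 4 and 3. For one unrelated miRNA split at the median, the chance that all responders fall on one side is 2 × C(11,4)/C(22,4) = 660/7,315 = 9% for 4 of 22. For 3 of 11 split 5/6 it is [C(5,3) + C(6,3)]/C(11,3) = 30/165 = 18%. Selecting among several miRNAs or cut-offs would raise these chances, but the SAP does not state how many miRNAs there are. The 20% and 28% rates also belong to the combined endpoint, so the figures bear on only two of the six tables.

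**Conclusion.** The point holds as a minor specification fault in an exploratory analysis. The one method in the text cannot show whether the pre-treatment miRNA profile differs between responders and non-responders, although Day 0 is one of the three time points the endpoint names. Six listed tables are titled for a different analysis, which needs miRNA groups and a visit that the SAP does not define.

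This rests on two things: Day 0 is the only miRNA sample before dosing, as note 5 to Table 1-1 indicates, and the comparison is with table titles, because the shells were not available. Section 5 reports no departure from the protocol's analyses and does not settle which of the two miRNA analyses is meant. The primary comparison with historical control, its significance level and the sample size are untouched.

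**What to change.** Replace the miRNA sentence in section 4.3.2 with wording such as:

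*For each miRNA, the median level at Day 0, Week 15 and Week 48, and the median change from Day 0 to Week 15 and to Week 48, will be summarised by response status, by treatment group and overall; Week 48 values are concurrent with the outcome.*

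Retitle the six tables to match, for example as miRNA level and change by Week 48 response status, with status taken from each table's own endpoint. All three named visits then have a level summary, and no miRNA cut-off is needed.

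If the incidence tables are wanted instead, the SAP would have to state the markers, the visit and the cut-offs before the results are seen. Level summaries would still be needed for any visit not used to form the groups.

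The cost is one sentence, six titles with their shells, and a few more descriptive rows. The samples are already in the schedule.
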